4.0 SYNOPSIS

Protocol Number	DSXS 1538a
Title	An Open-Label, Safety Study to Assess the Potential for Adrenal Suppression Following Maximal Use Treatment with Desoximetasone 0.25% Shampoo (Taro Pharmaceuticals U.S.A., Inc.) in Patients with Moderate to Severe Scalp Psoriasis
Objectives	
The objectives of this study are to:
 
1. Evaluate the potential of desoximetasone 0.25% shampoo to suppress HPA axis function in patients with moderate to severe scalp psoriasis.2. Evaluate the efficacy parameters and adverse event (AE) profiles of desoximetasone 0.25% shampoo administered to patients with moderate to severe scalp psoriasis.
Sponsor	Taro Pharmaceuticals U.S.A., Inc.
Name of Test Product	Desoximetasone 0.25% shampoo
Route of Administration	Topical
Study Design	An open-label, safety study to assess the potential for adrenal suppression following maximal use treatment with desoximetasone 0.25% shampoo applied once-daily for 28 days in adult patients with moderate to severe scalp psoriasis. Each patient is expected to receive 28 doses of study product.
Study Population	Up to 40 patients will be enrolled to obtain 20 evaluable male or female patients 18 years of age or older with a confirmed diagnosis of moderate to severe plaque psoriasis of the scalp with $\geq 25\%$ scalp affected.
Study Conduct	All patients will attend the clinic for 3 scheduled visits and a telephone follow-up phone call (Visit 4): Visit 1: Screening /Enrollment (Day 1) Visit 2: Interim Visit (Day 14 ± 2) Visit 3: End of Study (Day 29 ± 2) or Early Termination Visit 4: Follow Up (Day 42 ± 4) Telephone Phone Call If 10 or more patients experience biochemical abnormal values suggestive of possible HPA axis suppression, enrollment will be stopped. Such abnormality is defined by a 30 minute post Cortrosyn™ injection level cortisol level of ≤ 18 mcg/100ml during the Cortisol Response Test.
Inclusion Criteria	
1. Male or non-pregnant, non-lactating females 18 years of age or older.2. If female and of childbearing potential, prepared to abstain from sexual

CONFIDENTIAL PROTOCOL

An Open Label, Safety Study to Assess the Potential for Adrenal Suppression Following Maximal Use Treatment with Desoximetasone 0.25% shampoo(Taro Pharmaceuticals U.S.A., Inc.) in Patients with Scalp Psoriasis

	
intercourse or use a reliable method of contraception during the study (e.g., condom, IUD, oral, transdermal or injected hormonal contraceptives). Female patients using hormonal contraceptives should have been on the same product/dosing regimen for at least 28 days before baseline and should not change this regimen during the study.
 
3. IRB-approved, signed informed consent form that meets all criteria of current FDA regulations.4. Patients with a confirmed clinical diagnosis of stable plaque psoriasis of the scalp with $\geq 25\%$ scalp affected.5. Investigator Global Assessment (IGA) score of 3 (Moderate) or 4 (Severe).
Exclusion Criteria	
1. Females who are pregnant, nursing, planning to become pregnant during the duration of the study, or if of child-bearing potential and sexually active and not prepared to use appropriate contraceptive methods to avoid pregnancy.2. Patients < 18 years of age.3. Patients whose scalp psoriasis necessitates systemic or other concomitant topical therapies during the study. Concomitant treatment of body psoriasis with OTC topical products, including emollients, is allowed.4. IGA score < 3.5. Scalp psoriasis with $< 25\%$ scalp affected.6. History of psoriasis that has been unresponsive to topical corticosteroid therapy.7. Patient has a scalp skin condition that would interfere with the diagnosis or assessment of plaque psoriasis of the scalp (e.g., seborrheic dermatitis, eczema, cutaneous T-cell lymphoma, or other forms of psoriasis including guttate, inverse, pustular or erythrodermic psoriasis).8. History of an adverse reaction to CortrosynTM or similar test reagents9. Presence of pigmentation, extensive scarring, pigmented lesions, or sunburn in the treatment areas that could interfere with the rating of efficacy parameters, including planned extensive exposure to sunlight during the study.10. History of allergy or sensitivity to corticosteroids or history of any drug hypersensitivity or intolerance which, in the opinion of the Investigator, would compromise the safety of the patient or the results of the study.11. Patient has a significant history or current evidence of chronic infectious disease, system disorder, organ disorder or insufficiency, immunosuppression (from medical treatment or disease), organ transplant or other medical condition that, in the Investigator's opinion, would place the study patient at undue risk by participation in the study.12. Patient is currently receiving or has received any radiation therapy or

CONFIDENTIAL PROTOCOL

An Open Label, Safety Study to Assess the Potential for Adrenal Suppression Following Maximal Use Treatment with Desoximetasone 0.25% shampoo(Taro Pharmaceuticals U.S.A., Inc.) in Patients with Scalp Psoriasis

	anti-neoplastic agents within 3 months before baseline.
13.	Known history of hypothalamic-pituitary-adrenal axis impairment or any other disturbance of the adrenal function (e.g. Cushing or Addison disease).
14.	Known or suspected severe renal insufficiency or severe hepatic disorders or severe heart disease.
15.	Patients who have a history of or current diagnosis of glaucoma or posterior subcapsular cataracts or any other ocular condition that, in the opinion of the Investigator, would place study patient at undue risk.
16.	Patients who have had surgery on the eyes or eyelids within 1 month before baseline or plan to have eye or eyelid surgery during the study.
17.	Patients with active infection (including but not limited to bacterial, fungal and viral infection) and/or open wounds on the entire head and neck area.
18.	Use within 4 weeks before baseline of 1) oral or intravenous corticosteroids, 2) UVA/UVB therapy, 3) PUVA (psoralen plus ultraviolet A therapy, 4) topical tacrolimus, 5) topical pimecrolimus, 6) systemic retinoids or 7) any other systemic psoriasis treatment
19.	Use of tanning booths or nonprescription UV light source within 2 weeks before baseline.
20.	Use within 8 weeks before baseline of 1) immunomodulators or immunosuppressive therapies or 2) interferon.
21.	Use within 14 days before baseline of calcipotriene or other Vitamin D preparations.
22.	Changed brands/types or frequency of use of routine hair care products (shampoo, conditioner, sprays etc.) within 14 days before baseline, or intend to change during the study.
23.	Use of systemic antibiotics or prescription-strength systemic anti-inflammatory agents within 1 month before baseline.
24.	Use of the following within 2 weeks before baseline: 
Topical anti-psoriatic agents.Topical corticosteroids.Topical retinoids.Topical anti-inflammatory agents.Medicated shampoos for scalp psoriasis (including coal tar shampoo).New regimens of beta blockers.Lithium preparations.Anti-malarial agents.
25.	Patient has been treated within 12 weeks before baseline with any

CONFIDENTIAL PROTOCOL

An Open Label, Safety Study to Assess the Potential for Adrenal Suppression Following Maximal Use Treatment with Desoximetasone 0.25% shampoo(Taro Pharmaceuticals U.S.A., Inc.) in Patients with Scalp Psoriasis

	
biological therapies for psoriasis.
 
26. Inability to understand the protocol requirements, instructions, and study-related restrictions, the nature, scope, and possible consequences of the clinical study.
 
27. Unlikely to comply with the protocol requirements, instructions, and study-related restrictions, such as uncooperative attitude, inability to return for follow-up visits, and improbability of completing the clinical study.
 
28. Receipt of any drug as part of a research study within 30 days before baseline.
 
29. The patient is a member of the investigational study staff or a member of the family of the investigational study staff.
 
30. Previous participation in this study.

Criteria for Evaluation	
Primary Outcome Measures:
 
Hypothalamic Pituitary Adrenal (HPA) Axis Response to Cosyntropin demonstrating the absence or presence of adrenal suppression at the end of treatment defined by the following criteria: 30 minute post Cortrosyn™ injection level cortisol level of ≤ 18 mcg/100ml during the Cortisol Response Test
 
Secondary Outcome Measures:
 
Hypothalamic Pituitary Adrenal (HPA) Axis Response to Cosyntropin demonstrating the presence of adrenal suppression at the end of treatment with % Scalp Affected as a covariate

HPA Axis Evaluation	
If at the end of the study the patient has a cortisol response test that is suggestive of HPA axis suppression, they will have a follow up test at least every 4 weeks in accordance to the follow up calendar in Appendix D or until such time as the Investigator considers the adrenal function has turned to normal.
 
Patients with normal adrenal function at baseline will be included in the HPA Axis evaluation.
 
Primary Analysis:
 
Proportion of patients in the study with HPA axis suppression following treatment with the study medication.
 
Secondary Analysis:
 
A logistic regression of the proportion of patients in the study with HPA axis suppression will be performed with % scalp affected as a covariate.

Safety Parameters	Adverse events will be classified using standard MedDRA terminology Version 19 or higher and summarized over all patients. Adverse events reported during the study will be tabulated in summary table by type, date of onset, date of resolution, incidence, severity, action taken, outcome and Investigator's opinion of relationship to the study product will be prepared by

CONFIDENTIAL PROTOCOL

An Open Label, Safety Study to Assess the Potential for Adrenal Suppression Following Maximal Use Treatment with Desoximetasone 0.25% shampoo(Taro Pharmaceuticals U.S.A., Inc.) in Patients with Scalp Psoriasis

	
treatment group. Signs and symptoms of scalp psoriasis will not be considered adverse events, unless in the Investigator's opinion, they have increased in frequency and/or severity to such an extent that the Investigator/patient considers that it is in the patient's best interest to be dropped from continued participation in the study and given alternative therapy for their condition.
 
Concomitant medication use during the study will be tabulated by patient. Ocular safety evaluations will be assess at the discretion of the Investigator based on the findings of the HEENT exam performed at each visit along with the ocular discomfort reported by the patient. Ocular discomfort will be assessed by the patients and reported to staff during clinic visits.

Sample Size Determination	The sample size of 20 evaluable patients was deemed appropriate to meet the objectives of the study.

CONFIDENTIAL PROTOCOL

An Open Label, Safety Study to Assess the Potential for Adrenal Suppression Following Maximal Use Treatment with Desoximetasone 0.25% shampoo(Taro Pharmaceuticals U.S.A., Inc.) in Patients with Scalp Psoriasis

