9.0 INVESTIGATIONAL PLAN

9.1 Study Design and Plan Description

This open-label, safety study is designed to evaluate the potential for adrenal suppression after maximal use treatment with desoximetasone 0.25% shampoo (Taro Pharmaceuticals, U.S.A.), for the treatment of moderate to severe scalp psoriasis.

Up to 40 eligible patients with stable plaque psoriasis of the scalp that satisfy all eligibility criteria will be enrolled into the study at Visit 1 to obtain 20 evaluable patients. Patients must be overall in good health. They should have a current diagnosis of moderate to severe scalp psoriasis with IGA score of at least 3 or 4.

Up to 40 patients will be enrolled to obtain 20 evaluable patients with a confirmed diagnosis of moderate to severe scalp psoriasis.

Patients enrolled in the study will apply product once daily for 28 days, according to provided instructions. Each patient is expected to receive 28 doses of study product.

Patients will attend a total of 3 Clinic Visits and a telephone follow-up phone call (Visit 4) as follows:

- **Visit 1 (Day 1):** Screening/Enrollment
- **Visit 2 (Day 14±2):** Interim Visit
- **Visit 3 (Day 29 ± 2):** End of Study or Early Termination
- **Visit 4 (Day 42± 4):** Follow-Up Telephone Phone Call

The primary endpoint is the proportion of patients in the study with HPA axis suppression following treatment with the study medication.

The safety profile of each treatment group will be evaluated by comparing adverse events.

Ethical consideration related to this protocol and the use of human patients will be reviewed by an IRB.

CONFIDENTIAL PROTOCOL

An Open Label, Safety Study to Assess the Potential for Adrenal Suppression Following Maximal Use Treatment with Desoximetasone 0.25% shampoo(Taro Pharmaceuticals U.S.A., Inc.) in Patients with Scalp Psoriasis

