9.5.1 Visit 1: Screening/Enrollment (Day 1), before 12 pm

1. **Informed Consent:** Patients who are willing to comply with study procedures will read and sign the informed consent form.
2. **Medical History and Demographics:** Review the patient's demographic and medical history including concomitant medication use within the last 12 weeks.
3. **Physical Examination:** A general physical exam will be conducted.
4. **HEENT Examination:** A general exam of the head, eyes, ears, nose and throat will be conducted at the clinic.
5. **% Scalp Affected:** Patient's scalp will be examined by Investigator/designated clinician to determine the percent surface area affected with plaque psoriasis. Refer to Appendix B.

CONFIDENTIAL PROTOCOL

An Open Label, Safety Study to Assess the Potential for Adrenal Suppression Following Maximal Use Treatment with Desoximetasone 0.25% shampoo(Taro Pharmaceuticals U.S.A., Inc.) in Patients with Scalp Psoriasis

6. **Vital Signs:** The patient's vital signs will be recorded (pulse, blood pressure, temperature and respiration rate).
7. **Pregnancy Test:** A pregnancy test will be required of all females of child bearing potential prior to enrollment.
8. **Investigator's Global Assessment:** Patient's scalp will be examined to determine a psoriasis severity score based on a global assessment of plaque elevation, scaling and erythema by the Investigator/designated clinician (refer to Appendix A). Patients with a score of 3 or more, indicating moderate to severe psoriasis will be included in the study.
9. **Concomitant Medication:** Review with the patient use of concomitant medication within the last 12 weeks.
10. **Confirm Inclusion/Exclusion Met:** Confirm the patient meets all inclusion/exclusion criteria.
11. **Laboratory Evaluations:** A blood sample will be collected for hematology and clinical chemistry testing. (See Appendix F).
12. **Cortisol Response Test:** All patients will have a cortisol response test performed according to the procedure detailed in Appendix D.
13. **Dispense Study Product:** If patient is eligible to enroll, record the weight of one bottle of study product and dispense with instructions.
14. **Provide Dosing Diary:** Provide diary and instruct patient regarding how it is to be filled out and how study product is to be used.
15. **Provide Patient Wristband:** Each patient will receive a wristband to indicate that the patient is using a medication that has the potential to cause HPA axis suppression.

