9.6.18 Cortisol Response Test

At Visit 1 and Visit 3 all patients will have a cortisol response test performed according to the procedure detailed in Appendix D. The resulting blood sample should be sent to ACM Global Laboratory for immediate testing.

The test at the End of Study visit should not be performed if the patient dosed within 12 hours.

A patient will be considered to have normal basal cortisol level and adrenal function if they meet all three criteria listed below under Normal. Failure to meet any of these criteria is indicative of abnormal adrenal function or potential HPA axis suppression, even in absence of related symptoms (e.g. nausea, headache, myalgia, fatigue or loose stool); for abnormal results, the patient will be monitored in accordance to the follow-up schedule below.

	Cortisol Results	
	Normal	Abnormal
Basal (pre Cortrosyn™ injection)	≥ 5 mcg/100ml	< 5 mcg/100ml
30 minutes post Cortrosyn™ injection	≥ basal value + 7	< basal value + 7
	> 18 mcg/100ml	≤ 18 mcg/100ml

HPA Axis suppression will be defined as a 30 minute post Cortrosyn™ injection level cortisol level of ≤ 18 mcg/100ml. If the Visit 1 Cortisol Response Test shows signs of HPA axis suppression as defined above the patient will be contacted and instructed to discontinue the use of study product, not to initiate any new steroid therapy, topical or otherwise and an End of Study Visit will be scheduled to conduct a Cortisol Response Test at least 28 days after the initial Cortisol Response Test at Visit 1 to assess for HPA axis suppression. At Visit 3 the study treatment period will be over, any patients with results of HPA axis suppression will be advised not to initiate any new steroid therapy, topical or otherwise, and to return to the site in 28 days at which time they will be assessed for HPA axis suppression.

CONFIDENTIAL PROTOCOL

An Open Label, Safety Study to Assess the Potential for Adrenal Suppression Following Maximal Use Treatment with Desoximetasone 0.25% shampoo(Taro Pharmaceuticals U.S.A., Inc.) in Patients with Scalp Psoriasis

Any patient presenting with symptoms of HPA axis suppression, such as nausea, headache, myalgia, fatigue or loose stool, will be referred to an endocrinologist. As an additional safety precaution, wristbands identifying the patient as someone suffering from adrenal suppression secondary to steroid withdrawal will be provided to alert medical personnel should any emergencies arise before adrenal function returns to normal.

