10.1.1 Determination of Sample Size

The sample size of 20 evaluable patients was deemed appropriate to meet the objective of the study.

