## **6.2 Statistical Analyses**

### **6.2.1 Safety Analysis of Potential HPA Axis Suppression**

Dosing will be once daily for 28 days. Patients who have normal adrenal function at baseline, use at least 21 doses of the study product and have data from a post-treatment cortisol response test will be included in the analysis.

The primary analysis of interest is to assess the proportion of patients considered to have demonstrated possible HPA axis suppression following treatment with the study medication.

A logistic regression of the proportion of patients in the study with HPA axis suppression may be performed as exploratory analysis with % scalp affected as a covariate. This will depend on the distribution of the % scalp data collected. See Appendix D for results from the cortisol response test considered indicative of potential HPA axis suppression.

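### Normal baseline adrenal function decides who enters the primary analysis but not who is enrolled or given product, and the Visit 1 stop instruction uses a narrower definition

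*Protocol*

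**What the plan says.** **Analysis.** The synopsis states "Patients with normal adrenal function at baseline will be included in the HPA Axis evaluation". Protocol 10.1.2 and SAP 6.2.1 carry the same condition. The SAP admits "Patients who have normal adrenal function at baseline, use at least 21 doses of the study product", and also requires a post-treatment cortisol test. Protocol 9.6.18 and Appendix D define the term: "A patient will be considered to have normal basal cortisol level and adrenal function if they meet all three criteria listed below under Normal". The three are a basal value of at least 5 mcg/100ml, a 30-minute value at least 7 above basal, and a 30-minute value above 18.

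**Entry.** The nearest criterion is exclusion 13: "Known history of hypothalamic-pituitary-adrenal axis impairment or any other disturbance of the adrenal function". Exclusions 18 and 24 add washouts for oral or intravenous corticosteroids (4 weeks) and topical corticosteroids (2 weeks). No criterion refers to a Visit 1 cortisol value.

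**Sequence.** Section 5.0 puts screening, enrolment, the cortisol test and dispensing on Day 1. In section 9.5.1 the test is step 12, and step 13 reads "If patient is eligible to enroll, record the weight of one bottle of study product and dispense with instructions". Under Appendix D the samples go to an outside laboratory the same day.

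**Stopping.** If the Visit 1 test shows suppression, "the patient will be contacted and instructed to discontinue the use of study product", with a retest at least 28 days after the first test (9.6.18, Appendix D; repeated in SAP Appendix D). The sentence just before defines suppression by the 30-minute value of 18 or less alone.

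**Numbers.** "The sample size of 20 evaluable patients was deemed appropriate to meet the objective of the study". "Up to 40 patients will be enrolled to obtain 20 evaluable patients". Section 9.3.4 says that withdrawn or removed patients are not replaced.

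**The concern.** Four decisions depend on baseline adrenal function: whether the patient may enter, whether product is handed over, whether product is stopped, and whether the patient counts in the primary analysis. Only the last uses the full three-part definition. The first two do not use the test at all, and the third uses one part of it.

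Two groups can therefore receive the corticosteroid under study although their Visit 1 test has already put them outside the primary analysis. One group is to be stopped once the result arrives. The other, on the literal wording, is not stopped. At stake is exposure that the plan's own rule makes avoidable, and a count of evaluable patients that depends on a result nobody has at enrolment.

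**Working it through.** **Step 1: the rules side by side.**

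| Decision | Where | Baseline rule applied |
|---|---|---|
| Entry | Protocol 4.0, 9.3.1, 9.3.2 | Known history only; no test result |
| Dispensing | Protocol 5.0, 9.5.1 | Same visit as the test; result not awaited |
| Stopping | Protocol 9.6.18, Appendix D; SAP Appendix D | 30-minute value of 18 or less |
| Primary analysis | Protocol 4.0, 10.1.2; SAP 6.2.1 | All three criteria met |

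**Step 2: Visit 1 results run through these rules.**

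| Visit 1 result | Dispensed | Told to stop, on the literal text | In primary analysis |
|---|---|---|---|
| All three criteria met | Yes | No | Yes, if at least 21 doses and a post-treatment test |
| 30-minute value at or below 18 | Yes | Yes, once the result is communicated | No |
| 30-minute value above 18, basal or increment criterion failed | Yes | No | No |

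**Step 3: the third row is a real category.** With basal value b, a patient passes the 18 criterion and fails the increment when the 30-minute value lies above 18 and below b + 7. This is possible whenever b + 7 > 18, that is b > 11. A patient with b < 5 and a 30-minute value above 18 has risen by more than 18 − 5 = 13, so meets the increment and fails on the basal value alone. SAP listing L16.2.6.1 has separate columns for abnormal adrenal function and for suppression, and its shell shows a Visit 3 row with yes for the first and no for the second.

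**Step 4: the evaluable target.** The figure of 20 cannot be reproduced, because no precision target, suppression rate or non-evaluable rate is stated. The cap allows 1 − 20/40 = 50% non-evaluable. If each of 40 patients is evaluable with probability q, the exact binomial probability of at least 20 evaluable is 0.998 at q = 0.7, 0.926 at 0.6, 0.787 at 0.55 and 0.563 at 0.5.

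Let f be the Visit 1 failure rate and d the later loss. Both are assumptions, since the documents give neither. Expected evaluable = 40 × (1 − f) × (1 − d). With d = 20%:

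- f = 10%: 40 × 0.9 × 0.8 = 28.8
- f = 30%: 40 × 0.7 × 0.8 = 22.4
- f = 40%: 40 × 0.6 × 0.8 = 19.2

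The expectation falls below 20 only when f exceeds 1 − 20/(40 × 0.8) = 37.5%.

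**Step 5: patients dispensed product although outside the analysis from Visit 1.** Expected enrolment for 20 evaluable is 20/[(1 − f)(1 − d)], and a share f of these are Visit 1 failures. With d = 10%:

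| f (assumed) | Enrolled and dispensed | Of these, Visit 1 failures |
|---|---|---|
| 5% | 20/0.855 = 23.4, so 24 | 1.2 |
| 10% | 20/0.81 = 24.7, so 25 | 2.5 |
| 20% | 20/0.72 = 27.8, so 28 | 5.6 |
| 30% | 20/0.63 = 31.7, so 32 | 9.5 |

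For comparison, if only patients with a normal result were dispensed product, 20/0.9 = 22.2, so 23, would receive it at any f. The number tested at screening would stay at 24 to 32. The documents do not allow the failures to be divided between rows 2 and 3 of Step 2.

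**The case against.** The strongest reply is that the sponsor saw this and dealt with it. Revision 1 documented the Visit 1 stopping criteria, and Revision 2 raised enrolment to 40 so that 20 evaluable could be reached. Samples are for immediate testing, and every patient receives a warning wristband at Visit 1. The exclusion uses a pre-treatment value, so it does not bias the primary proportion among patients with a normal baseline. Section 9.6.18 also treats failure of any criterion as potential suppression and sends abnormal results to the follow-up schedule.

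Much of this stands. It limits exposure for patients at or below 18, and it answers the concern about yield. It does not close the gap for the third row. The stop instruction points back to a definition, and the nearest one is the 18 criterion alone. The follow-up schedule counts days after discontinuation, so it presupposes a stop that the text has not instructed for this group. That is an ambiguity and should be described as one; a site could read it either way.

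The order of steps within Visit 1 should not carry the argument. Section 9.5.1 confirms eligibility before the cortisol test, while the section 5.0 schematic lists it after. What matters is dispensing on the same day.

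A reader might infer four stronger things, none of which the documents support:

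- **The target of 20 is in danger.** This needs a failure rate that the documents do not give and, at 20% later loss, one above 37.5%.
- **Waiting for the result would yield 40 × 0.8 = 32 evaluable from the same cap.** This only moves failures outside the cap. Filling 40 places would mean testing 40/(1 − f) patients: about 44, 57 and 67 at f = 10%, 30% and 40%.
- **These patients are exposed to no purpose.** Anyone with one dose enters the safety population (Protocol 10.2, SAP section 5), and the adverse event profile is a stated objective.
- **They have impaired adrenal function.** The package insert in Appendix G says that a low basal level does not by itself establish insufficiency, and that many people with normal function respond less than expected.

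**Conclusion.** The point holds as a mismatch between rules. The primary analysis requires all three cortisol criteria at baseline, entry and dispensing require no test result, and the stop instruction on its literal wording requires only the third criterion. A patient failing only the basal or increment criterion can be treated for 28 days while outside the primary analysis. A patient at or below 18 has product for an unstated time until the result is communicated.

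The size cannot be fixed from the documents. Under an assumed 10% later loss and 5% to 30% Visit 1 failures, about 1 to 10 such patients are dispensed product for every 20 evaluable. The finding rests on avoidable exposure and inconsistent definitions. It does not show a shortfall in evaluable patients, bias in the primary proportion, or impaired adrenal function in those affected.

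**What to change.** Reconcile four sets of passages so that one definition of normal baseline adrenal function governs entry, dispensing, stopping and inclusion in the analysis:

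- the entry criteria (Protocol 4.0, 9.3.1, 9.3.2);
- the Visit 1 sequence (Protocol 5.0, 9.5.1);
- the Visit 1 stop instruction (Protocol 9.6.18 and Appendix D, with the copy in SAP Appendix D);
- the evaluability rule (Protocol 10.1.2, SAP 6.2.1).

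The sponsor decides what the clinical rule is; this point asks only that the passages agree. Also state whether a Visit 1 failure counts towards the cap of 40, and how that fits with the no-replacement sentence in 9.3.4.

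**Cost.** A protocol amendment and a matching SAP edit. No new test is needed, because the cortisol test is already done at Visit 1. If the reconciled rule makes dispensing wait for the result, there is a short wait and probably one added dispensing contact or visit, since weighing, instructions, diary and wristband are now handled at Visit 1. Day 1 and the washout windows before baseline would then need re-anchoring.
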